#### 8.21.5. Pregnancy

Details of all pregnancies in female participants and, if indicated, female partners of male participants will be collected from study specific informed consent and until the last study assessment as outlined in the SoA. If a pregnancy is reported, the Investigator should inform the sponsor within 24 hours of learning of the pregnancy and should follow the procedures outlined in Appendix 10.3.

Abnormal pregnancy outcomes (e.g., spontaneous abortion, foetal death, stillbirth, congenital anomalies, ectopic pregnancy) are considered SAEs.

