#### 1.1.7.1. Part 1 Interventions & Duration

The total duration of study participation for a participant is up to approximately 50 days, with the following sequence and duration of study periods:

- **Screening** phase: from Day -28 to Day -1 pre-admission (Historical generic screening data collected through the hVIVO Generic Screening process may be transferred to this study after the study-specific consent form has been signed by the participant)
- **Inpatient phase:** Participants will be resident in the Unit for 1 days (from Day 0 to Day +1). Procedures will include:
  - o Admission to Unit on Day 0
  - Study intervention Intravenous (I.V.) dosing on Day 0
  - o Post infusion monitoring and PK Day 0 and Day 1
  - Participants will be discharged from the Unit on Day 1 (or may remain longer at the Principal Investigator's discretion)
- Outpatient phase: study assessments will be conducted at follow up clinic visits and telephone calls as follows:
  - O Clinic visits: Day 2, Day 3, Day 7 (±1 day) and Day12
  - o Final safety follow-up by telephone: Day 18 (±3 days).

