#### 2.3.1. Risk Assessment

The known risks to participants are detailed in Table 1. However, there may also be risks that are unforeseen and not anticipated (e.g., unknown allergies). Every effort will be made to monitor the health of the participants to ensure that such risks are minimised. Trained medical personnel and facilities will be available to provide medical emergency care.

Table 1 - Risk Assessment

Potential Risk of Clinical Significance	Rationale for Risk	Mitigation Strategy		
	Study Intervention			
	Local signs and symptoms associated with the injection may include: erythema, swelling/induration, and pain/tenderness at the injection site.	Local reactions will be monitored but are generally short-term and do not require treatment.		
	Other side effects include rash	Side effects will be monitored but are generally short-term and do not require treatment.		
Intravenous Dosing with Palivizumab	Other less common but serious side effects reported include anaphylaxis and anaphylactic shock and other severe acute hypersensitivity reactions	Medications (e.g epinephrine) will be available in the clinic to treat serious allergic reactions promptly. Participants with a known allergy, or history of anaphylaxis or other serious adverse reactions will be excluded from the study. The study site should have medical treatment available in case of severe allergic reactions.		
	Systemic exposure to Palivizumab	To minimise any risks associated with systemic exposure to Palivizumab, male and female participants must be on highly effective contraception methods during the study and up to 90 days post dosing with Palivizumab.		
	Lack of pre-clinical reproductive toxicity evaluation as well as clinical toxicity evaluations in pregnancy due to target population indication (high-risk children <24 months) of Palivizumab and requirements for licensing for indication. Although reproductive toxicity studies are	Participants will be advised to use appropriate methods of contraception during the study and for 90 days after administration of Palivizumab for male participants (equivalent to the sperm life cycle) and 30 days for female		

Potential Risk of Clinical Significance	Rationale for Risk	Mitigation Strategy	
	not considered appropriate for the study intervention.	participants (equivalent to the length of a menstrual cycle).	

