#### 4.1.4. Part 2 duration

The total duration of study participation for a participant is up to approximately 122 days, with the following sequence and duration of study periods:

- **Screening** phase: from Day -90 to Day -4 pre-quarantine admission (Historical generic screening data collected through the hVIVO Generic Screening process may be transferred to this study after the study-specific consent form has been signed by the participant).
- **Inpatient phase:** Participants will be resident in the Quarantine Unit for approximately 16 days (from Day -3 to Day +12). Procedures will include:
  - o Pre-HVC:
- Admission to Quarantine Unit on Day -3
- Study intervention I.V. dosing on Day -1
- o HVC:
- Challenge Virus inoculation on Day 0 (window 1 to 2 days post-treatment)
- Post-HVC
- Day 0 onwards and each day study assessments will be conducted as per Schedule of Activities
- Participants will be discharged from the Quarantine Unit on Day12 (or may remain longer at the Principal Investigator's discretion)
- Outpatient phase: study assessments will be conducted
  - Clinic visit for PK sample on Day 20 (±2 days)
  - Final safety follow-up visit(s): Day 28 (±3 days)

The study will be conducted by hVIVO which has extensive experience with RSV challenge studies. Numerous studies have been performed using experimental RSV infection in human participants. To date, in hVIVO's studies, over 1220 healthy participants (18 to 55 years of age) have been successfully and safely inoculated with RSV-A Memphis 37b. These studies demonstrated that adults could be infected by nasal inoculation and that experimental infection was safe. This strain has been shown to cause symptoms and virus shedding that closely match natural infection.

Administration of study intervention and challenge with RSV-A Memphis 37b will take place in hVIVO's specialised Clinical Units, either in the Quarantine Unit or Screening Clinic Units. Standard study procedures (including collection of blood, urine, and nasopharyngeal secretions for assessment of safety and efficacy) have been employed in previous studies conducted by hVIVO.

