# 5.1. Inclusion Criteria

Participants are eligible to be included in the study only if all of the following criteria apply:

NO	INCLUSION CRITERIA			
1	An informed consent document signed and dated by the participant and the Investigator.			
2	Aged between 18 and 55 years old on the day of signing the consent form.			
3	In good health with no history, or current evidence, of clinically significant medical conditions, and no clinically significant test abnormalities that will interfere with participant safety, as defined by medical history, physical examination, (including vital signs), Electrocardiogram (ECG), and routine laboratory tests as determined by the Investigator.			
4	A documented medical history prior to enrolment.			
5	The following criteria are applicable to female participants participating in the study.  a) Females of childbearing potential must have a negative pregnancy test prior to enrolment.  b) Females of non-childbearing potential:  a. Post-menopausal females; defined as having a history of amenorrhea for >12 months with no alternative medical cause, and /or by FSH level >40mIU/mL, confirmed by laboratory.  b. Documented status as being surgically sterile (e.g. tubal ligation, hysterectomy, bilateral salpingectomy and bilateral oophorectomy).			
6	The following criteria apply to female and male participants:  a) Female participants of childbearing potential must use one form of highly effective contraception. Hormonal methods must be in place from at least 2 weeks prior to the first study visit. The contraception use must continue until 30 days after the date of viral challenge/last dosing with IMP (whichever occurs last). Highly effective contraception is as described below:  a. Established use of hormonal methods of contraception described below (for a minimum of 2 weeks prior to the first study visit). When hormonal methods of contraception are used, male partners are required to use a condom with a spermicide:			

- i. combined (oestrogen and progestogen containing) hormonal contraception associated with inhibition of ovulation:
  - 1. oral
  - 2. intravaginal
  - 3. transdermal
- ii. progestogen-only hormonal contraception associated with inhibition of ovulation:
  - 1. oral
  - 2. injectable
  - 3. implantable
- b. Intrauterine device (IUD)
- c. Intrauterine hormone-releasing system (IUS)
- d. Bilateral tubal ligation

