- e. Male sterilisation (with the appropriate post vasectomy documentation of the absence of sperm in the ejaculate) where the vasectomised male is the sole partner for that woman.
- f. True abstinence sexual abstinence is considered a highly effective method only if defined as refraining from heterosexual intercourse during the entire period of risk associated with the study treatments. The reliability of sexual abstinence needs to be evaluated in relation to the duration of the clinical trial and the preferred and usual lifestyle of the participant.
- b) Male participants must agree to the contraceptive requirements below at entry to quarantine and continuing until 90 days after the date of Viral challenge / last dosing with the investigational medicinal product (IMP) (whichever occurs last):
  - a. Use a condom with a spermicide to prevent pregnancy in a female partner or to prevent exposure of any partner (male and female) to the IMP.
  - b. Male sterilisation with the appropriate post vasectomy documentation of the absence of sperm in the ejaculate (please note that the use of condom with spermicide will still be required to prevent partner exposure). This applies only to males participating in the study.
  - c. In addition, for female partners of child bearing potential, that partner must use another form of contraception such as one of the highly effective methods mentioned above for female participants.
  - d. True abstinence sexual abstinence is considered a highly effective method only if defined as refraining from heterosexual intercourse during the entire period of risk associated with the study treatments. The reliability of sexual abstinence needs to be evaluated in relation to the duration of the clinical trial and the preferred and usual lifestyle of the participant.
- c) In addition to the contraceptive requirements above, male participants must agree not to donate sperm following discharge from quarantine until 90 days after the date of Viral Challenge/last dosing with IMP (whichever occurs last).

For Part 2 of the study:

Sero-suitable to the challenge virus, as defined in the study Analytical Plan.

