#### **10.3.11. Pregnancy**

If a female participant or partner of a male participant becomes pregnant during [specify time period], this must be reported by the Investigator to the medical monitor and Study Monitor by telephone as soon as possible, in accordance with hVIVO's SOPs, and at the latest within 24 hours of becoming aware of the event.

Following the telephone notification, the Investigator must fully and accurately complete the appropriate pregnancy reporting form, which must be e-mailed to the pharmacovigilance department and the Study Monitor at the latest within 24 hours of becoming aware of the pregnancy.

Participants will be advised to contact their GP or a specialist, as appropriate.

Consent for follow-up of the pregnancy and pregnancy outcome will be sought from the pregnant study participant or the pregnant partner of the male study participant as applicable. Consent for follow-up will be documented on an hVIVO Pregnancy Follow-up ICF.

Provided that the appropriate consent is in place, information related to the pregnancy will be collected as per hVIVO's SOPs and the Sponsor's requirements. The completed reporting form(s) will be sent to the Sponsor for review and assessment, and subsequent reporting as required.

- A complete evaluation will be documented in the source data to permit transfer to the clinical database.
- An emergency request (Section 6.3) to break the blind for the appropriate study participant to
  ensure that further care can be based on the actual identity of the study treatment that the
  participant received.
- hVIVO will maintain contact with the participant for a protracted period of time, but certainly until
  after the birth, in order to assess for outcomes that may be reportable as related AEs, and for
  reporting to the Sponsor as appropriate.
- hVIVO in consultation with the participant will keep the participant's GP informed.
- All cases of foetal drug exposure via the parent as a study participant will be reported to the Sponsor and the REC.

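### Pregnancy collection ends about 62 days (Part 2) and 72 days (Part 1) before the men's contraception period does, and Section 10.3.11 leaves its reporting period as an unfilled placeholder

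*Protocol*

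**What the plan says.** **Collection window.** Protocol Section 8.21.5 covers female participants and, "if indicated, female partners of male participants will be collected from study specific informed consent and until the last study assessment" in the schedule of activities. It refers to Appendix 10.3 for procedures.

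**Last assessment.** For Part 1, Section 1.1.7.1 gives "Final safety follow-up by telephone: Day 18 (±3 days". For Part 2, Section 4.1.4 gives "Final safety follow-up visit(s): Day 28 (±3 days".

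**Contraception period.** In Section 5.1, criterion 6b binds men from entry and "continuing until 90 days after the date of Viral challenge / last dosing with the investigational medicinal product (IMP) (whichever occurs last". Criterion 6a says of women: "The contraception use must continue until 30 days after the date of viral challenge/last dosing with IMP", again whichever is later.

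**Reporting period.** Section 10.3.11 applies if a participant or partner "becomes pregnant during [specify time period". The bracket was never completed. It is template text and not a redaction: Section 10.3.10 carries a similar unfilled bracket for post-study SAEs.

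**What still applies later.** Section 10.3.11 also says "All cases of foetal drug exposure via the parent as a study participant will be reported" to the sponsor and the ethics committee, with no end date, and asks for contact until after the birth. Section 8.21.1 requires notification of a related SAE learned of at any time after discharge.

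**Reason for contraception.** Table 1 in Section 2.3.1 names "Lack of pre-clinical reproductive toxicity evaluation as well as clinical toxicity evaluations in pregnancy" and ties the men's 90 days to the sperm life cycle.

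**The concern.** The protocol sets a period during which conception is to be avoided, then stops asking about pregnancy well before that period ends. A partner pregnancy that began on Day 60, for example, would fall inside the men's contraception period but after the last scheduled contact in either part.

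The remaining routes depend on someone volunteering the information. Section 8.21.1 does not oblige investigators to seek events once participation ends. Section 10.3.1 does not count an uncomplicated pregnancy as an adverse event. The foetal-exposure duty in Section 10.3.11 can be acted on only when a pregnancy is known. Section 8.21 makes the investigator responsible for identifying all pregnancies, yet the protocol provides no contact for doing so after the last assessment.

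Two wording faults add to this. The placeholder leaves the investigator without a stated end to the reporting duty in Section 10.3.11. Section 8.21.5 also limits partner collection by *if indicated*, which it does not define; Sections 8.21 and 10.3.11 include partners without that limit.

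What is at stake is completeness of safety information in an area where the protocol says data are lacking. Estimates, power and error rates are not touched.

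**Working it through.** **Inputs**
- Part 2: dosing Day -1, challenge Day 0, last visit Day 28 ± 3 (Section 4.1.4). Challenge is the later event, so Day 0 starts the count.
- Part 1: dosing Day 0, last contact Day 18 ± 3 (Sections 1.1.7.1 and 4.1.3).
- Contraception: 90 days for men, 30 days for women (criteria 6b and 6a).

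**Check on where the last assessment falls.** The protocol's maximum durations, counted inclusively, should be reproduced.
- Part 2: Day -90 to Day 31 is 90 + 31 + 1 = 122 days. The protocol states about 122.
- Part 1: Day -28 to Day 21 is 28 + 21 + 1 = 50 days. The synopsis states about 50. Section 4.1.3 states 52, a small difference that does not bear on this point.

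The last assessments are therefore read correctly.

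**Gap = end of contraception period minus day of last assessment**

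| | Nominal | Range over ±3 days | Share of period |
|---|---|---|---|
| Men, Part 2 | 90 - 28 = 62 | 90 - 31 = 59 to 90 - 25 = 65 | 62/90 = 69% |
| Men, Part 1 | 90 - 18 = 72 | 90 - 21 = 69 to 90 - 15 = 75 | 72/90 = 80% |
| Women, Part 2 | 30 - 28 = 2 | 1 day over to 5 short | nominal |
| Women, Part 1 | 30 - 18 = 12 | 30 - 21 = 9 to 30 - 15 = 15 | 12/30 = 40% |

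Counting Part 2 from dosing instead would give 89 - 28 = 61 days for men, but the rule takes the later event.

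**Numbers involved.** Planned palivizumab recipients: 6 + 25 = 31. Planned participants who might be called: 6 + 50 = 56. Both are approximate and are not caps: Section 7.4 allows replacement, and Section 9.5 allows the sample size to rise after an interim look. The number of men is not given.

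**The case against.** The strongest reply is that no rule is broken. Contraception limits the risk of conception, a collection window defines active follow-up, and nothing in the protocol says the two must end together. Section 8.21.5 states a complete window, so the blank in Section 10.3.11 can be read as an editorial slip. Known foetal exposure is reportable without limit, abnormal pregnancy outcomes are SAEs, and related SAEs learned of later must be notified. Site procedures and consent pages are not in the file and may already tell participants to report pregnancies. Table 1 also attributes the missing reproductive data to the licensed population and says such studies were not considered appropriate.

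Most of this stands. It shows that the protocol is not contradictory and that late pregnancies are not excluded from reporting. It does not supply any step after the last assessment by which a pregnancy would become known, and material outside the protocol would not complete the protocol's own bracket.

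Two stronger readings are tempting:

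- A reader might infer that the protocol contradicts itself or lets exposed pregnancies go unreported. The later reporting duties rule that out.
- A reader might use the 17 to 20 day half-life in Section 4.3 to argue that drug still in the man's circulation puts a later pregnancy at risk. The documents do not say whether drug in a man reaches a partner or foetus, and Table 1 rests the 90 days on the sperm life cycle. Residual drug therefore lends no support here.

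**Conclusion.** The concern holds as a gap in active ascertainment. For men's partners, collection stops about 62 days early in Part 2 and about 72 days early in Part 1. For women the Part 1 gap is about 12 days, and the Part 2 gap is too small to matter. Section 10.3.11 needs completing in any case.

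The practical scale is small, with about 31 planned palivizumab recipients and an unknown share of men. The point is a cheap improvement to safety follow-up, and no efficacy result depends on it.

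The day counts are firm. That no other cover exists is less certain, because it rests on the protocol and SAP alone. The women's figures use the 30 days in criterion 6a. The row of Table 1 on systemic exposure gives up to 90 days after dosing for both sexes; if that governed, the women's gaps would be about 89 - 28 = 61 days in Part 2 and 90 - 18 = 72 in Part 1.

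**What to change.** - In Sections 8.21.5 and 10.3.11, set one collection and reporting period: to 30 days for women and 90 days for men, after the later of challenge and last dosing. This replaces the placeholder.
- Delete *if indicated* for partners.
- Instruct participants to report any pregnancy up to that date, with at most one later telephone call.
- Add this to both schedules of activities.
- State in Section 4.4 that the call does not define the end of the study.

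**Cost.** Short edits to the protocol, schedules and consent wording, and one later contact: about 56 calls as planned, more if participants are replaced or added, fewer if the instruction alone is used. No sampling is added.

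The Section 4.4 sentence matters. If the call counted as a visit, maximum participation would rise from 122 to 90 + 90 + 1 = 181 days in Part 2 and from 50 to 28 + 90 + 1 = 119 days in Part 1, and the end of the study would move by about 62 days. With it, some pregnancy collection continues after the formal end of the study, which the protocol should say openly.

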# 8.21.6. Disease-Related Events and/or Disease-Related Outcomes Not Qualifying as AEs or SAEs

Not applicable.

#### 8.22. Treatment of Overdose

For this study, any dose of any drug administered as part of the study greater than the dose prescribed by the protocol will be considered an overdose.

In the event of an overdose, the Investigator should:

- 1. Contact the Medical Monitor immediately.
- 2. Closely monitor the participant for any AE/SAE and laboratory abnormalities associated with overdose and participants will be clinically followed up until the AE has resolved.
- 3. Document the quantity of the excess dose as well as the duration of the overdose in the CRF.

The Sponsor is responsible for notifying the MHRA and REC of the potential serious breach within 7 days of becoming aware of it.

#### 8.23. Pharmacokinetics

Blood (plasma) samples for the evaluation of PK parameters of Palivizumab will be collected as outlined in section 8.19.3.

Blood samples will be transported, processed and stored in accordance with the AP, and analysed using a bioanalytical assay.

Drug concentration information that may unblind the study will not be reported to investigative site or blinded personnel until the study has been unblinded.

# 8.24. Pharmacodynamics

Pharmacodynamic parameters are not evaluated in this study.

### 9. Statistical Considerations

Venn Life Sciences will perform the statistical analysis for the study. Full details of the planned statistical analysis (including the Part 1 analysis) will be presented in the Statistical Analysis Plan (SAP). Any deviations from the SAP will be documented in the Clinical Study Report (CSR).

Part 1 data analysis will be reported after completion of Part 1, and based on these results, Part 2 of the study will commence.

## 9.1. Statistical Hypotheses

There are no statistical hypotheses for Part 1. For Part 2, the main hypothesis is that Intravenous (IV) treatment with Palivizumab will have a prophylactic effect on RSV disease, that will translate to a lower infection rate and/or lower clinical symptomatology and/or lower viral titres compared to placebo.

Considering that the objectives of Part 2 are not for demonstration of statistically significant differences between groups, formal hypothesis testing will be performed for the main endpoints, as described in Section 1.1.6. All tests will be two-sided, using a type-one error probability of 0.05. p-values between 0.05 and 0.10 will be considered as indicative of a trend. As this is an exploratory study, no adjustment for multiple testing will be performed.

#### 9.2. Sample Size Determination

#### 9.2.1. Part 1 sample size

Approximately 6 participants will be enrolled in Part 1 of the study for an estimated total of 6 evaluable participants. Six evaluable participants are considered sufficient to achieve the objectives of Part 1.

